4.7 Remote Study Visits

4.7.1 Screening and Baseline Procedures

In light of the coronavirus pandemic, we have outlined a plan to protect patients and staff during study visits.

The NYU Langone study team will minimize in-person contact with study participants. All assessments that can be completed remotely will, optionally, take place via WebEx, a secure video conferencing platform. Participants without access to a computer or stable internet will be able to come to [name] for screening visits, and all department outlined precautions for in-person visits will be followed.

If consent can take place remotely, study staff will review the electronic consent form and consent quiz with the participant over WebEx. Participants will be provided an electronic consent form to sign (in REDCap), and a copy will be sent to their email.

For outpatients, all screening assessments that can be conducted remotely will be completed via WebEx. If participants meet eligibility criteria according to those assessments, participants will be

CONFIDENTIAL

This material is the property of the NYU School of Medicine and Langone Medical Center. Do not disclose or use except as authorized in writing by the study sponsor

scheduled for an in-person visit at [name] / the Center for Brain Imaging at [name], with careful adherence to all institutional safety precautions and social distancing. The screening assessments that must be completed in-person include the following: vital signs, anthropometrics, physical exam, and collection of a urine specimen for toxicology analysis/pregnancy screening.

At the in-person Baseline visit, study staff will first complete the in-person assessments from the screening visits. Once these assessments have been reviewed by a Study MD/NP, and it has been determined that participants meet all IEC for the study, study staff will proceed with the baseline visit procedures.

4.7.2 Physical Exams / Laboratory Tests

Physical exams that were performed within the last 6 months and are documented in the medical record will be used to replace the in-person physical exam for patients unless medical history obtained by the research NP or MD suggests the possibility of a new medical condition with onset after the most recent physical exam.

A rapid urine drug screen and (for individuals assigned female at birth or with childbearing potential of childbearing age) a urine pregnancy test will be conducted by the research coordinator / research assistant or by clinical staff during the screening visit or prior to the baseline visit if the screening visit was conducted remotely. These results will be reviewed at the time of the visit with the study MD or NP. These results will be confirmed by also submitting urine samples to outpatient labs.

4.8 Subject Consent and Assent

All subjects will be evaluated by trained research coordinator or the nurse practitioner for capacity to consent and will be further evaluated by a licensed psychiatrist for safety and appropriateness to participate. Consent and assent will be completed by a trained coordinator or study clinician at [name]. In order to further ensure protection of privacy for this patient population, patients will not be contacted by any member of the research team unless they have agreed to hear about the research process beforehand from the initial treating clinician. Clinicians in the NYU Medical Center Emergency Psychiatric Service and Adult Inpatient Psychiatry Unit, Bellevue Hospital Emergency Psychiatry Service, Walk-in Clinic and Inpatient Units, NYU Student Health Clinic, NYU-Lutheran Hospital Emergency Service and Outpatient Psychiatry Clinics Outpatient Psychiatry Clinic, Inpatient Psychiatry Units and the Comprehensive Psychiatry Emergency Program at Bellevue Hospital will be provided with study information as well as a document listing the inclusion/exclusion criteria in order to facilitate recruitment. This will allow the initial treating clinicians to help identify potential subjects as well as provide interested individuals with basic study-related information. Potential subjects identified by the initial treating clinicians will be asked whether they would like to speak to a researcher. If the patient agrees, the initial treating clinician

CONFIDENTIAL

This material is the property of the NYU School of Medicine and Langone Medical Center. Do not disclose or use except as authorized in writing by the study sponsor

will then contact the study psychologist or trained study team member and they will determine whether the study clinician (psychologist or psychiatrist) will go and meet with the patient at that time or whether the patient will be scheduled for a screening visit at [name]. During this meeting, the study will be explained to the potential participant and in the event that the individual is interested in participating, s/he will then be given the consent form to read and review.

Bellevue Psychiatry Inpatient Unit only: [name], the Director of the Inpatient Unit, will assess the clinical appropriateness of the individual to participate in research and will assess the individual's capacity to consent. [name] or the MD/PhD level clinician / nurse practitioner will also perform an assessment of clinical appropriateness and capacity to consent for any individuals interested in participating. After a potential study participant agrees to sign consent, the remaining screening procedures, including the informed consent process (as outlined below), will take place on the inpatient unit at Bellevue.

Process of Consent: Patients who are interested in participating in the study will meet with a trained research coordinator, an MD/PhD level clinician, or the nurse practitioner, who will review the consent form and assess the patient's capacity for participation in research in accordance with our standardized research procedures. After signing consent, participants will be assessed for eligibility. Subjects' capacity for participation in research will be reviewed by the coordinators in addition to an MD/PhD level clinician or a nurse practitioner during the screening process. The study team member obtaining the informed consent will take steps to ensure that the participant is capable of consenting and participating in the study. The study team member will ensure that the individual understands the content and procedures of the study, their rights as a participant, and their right to discontinue participation at any time. Individuals who are not able to demonstrate this level of comprehension will be excluded from participation. In addition, the potential subject must also achieve a perfect score on a ten-item true/false quiz that asks questions about the study procedure and potential risks. After the consent form has been signed, the subject will be provided with a letter detailing study-related information and contact information for key study staff.

For Spanish Speaking Subjects: Spanish speaking subjects will be provided with certified translated consent forms and assent forms accompanied by a native Spanish speaking interpreter with training and understanding in medical terminology during study visits.

Consent Forms: Consent forms will be stored in a locked file cabinet in folders labeled with the patients study identification number. This file will be separate from any of the subject's study data in order to separate their data from any identifying information.

4.9 Early Withdrawal of Subjects

Participants will be advised verbally and in the ICF that they have the right to withdraw from the study at any time without prejudice or loss of benefits to which they are otherwise entitled. Participants may withdraw from the study at any time and for any reason, and are not obligated to provide the reason.

CONFIDENTIAL

This material is the property of the NYU School of Medicine and Langone Medical Center. Do not disclose or use except as authorized in writing by the study sponsor

The Investigator or Sponsor may discontinue a patient from the study in the event of an inter-current illness, AE, other reasons concerning the health or well-being of the patient, or in the case of lack of cooperation, non-compliance, protocol violation, or other administrative reasons. If a patient does not return for a scheduled visit, every effort should be made to contact the patient. In any circumstance, every effort should be made to document patient outcome, if possible. The Investigator should inquire about the reason for withdrawal and follow-up with the patient regarding any unresolved AEs.

Any reason for withdrawal given (or the failure to provide a reason) must be recorded in the source documentation and on the patient's electronic case report form (eCRF).

5 Study Drug

5.1 Description

The study drug (Levetiracetam 185mg, 500mg, or placebo) will be supplied in a blinded and pre-labeled package.

5.2 Treatment Regimen

At least 24 and maximum of 46 early psychosis patients will be randomized to a single oral dose of levetiracetam 185 mg, 500 mg or placebo, which will be administered at Baseline (Visit 2).

5.3 Method for Assigning Subjects to Treatment Groups

Randomization will be in a 1:1:1 ratio in blocks of random size (3 or 6), stratified by diagnosis (schizoaffective vs. schizophreniform/schizophrenia).

5.4 Preparation and Administration of Study Drug

Study drug dispensation will take place at the NYU Langone Investigational Pharmacy. In order to ensure blinding, the 185mg, 500mg and placebo will be prepared in identical capsules. Once a participant passes the screening procedures, the Investigator, study physician, or nurse practitioner will enter the prescription information into EPIC or write a prescription order to be submitted physically to the pharmacy. The study drug will be prepared in accordance with the randomization list which will be kept by the pharmacy. Study staff will retrieve the study drug from the pharmacy and a study physician or nurse practitioner will administer the drug.

5.5 Prior and Concomitant Therapy

Concomitant medications that are permitted during the study include Benadryl for sleep. Antipsychotics are not permitted due to interactions with neurotransmitters affected by levetiracetam.

5.6 Packaging

All capsules of the study drug will be received in one bulk shipment from Sentrix Pharmacy and Discount and will be stored at room temperature in a marked bottle at the NYU Langone Investigational Pharmacy.

CONFIDENTIAL

This material is the property of the NYU School of Medicine and Langone Medical Center. Do not disclose or use except as authorized in writing by the study sponsor

5.7 Blinding of Study Drug

The NYU Investigational Pharmacy will maintain a randomization list for study participants. All other study staff, aside from one designated unblinded study team member, will be blinded to the treatment groups. All study drug doses and placebo will be prepared in identical capsules in order to maintain blinding.

5.8 Receiving, Storage, Dispensing and Return

5.8.1 Receipt of Drug Supplies

Upon receipt of the of the study treatment supplies, an inventory must be performed and a drug receipt log filled out and signed by the person accepting the shipment at the NYU Langone Investigational Pharmacy. It is important that the designated study staff counts and verifies that the shipment contains all the items noted in the shipment inventory. Any damaged or unusable study drug in a given shipment (active drug or comparator) will be documented in the study files. The investigator must notify study sponsor of any damaged or unusable study treatments that were supplied to the investigator's site.

5.8.2 Storage

All study drug will be kept at the NYU Langone Investigational Pharmacy at room temperature. No special handling or storage requirements are indicated.

5.8.3 Dispensing of Study Drug

Regular study drug reconciliation will be performed by the study's unblinded pharmacist to document drug assigned, drug consumed, and drug remaining. This reconciliation will be logged on the drug reconciliation form, and signed and dated by the pharmacist. Administration of study drug during Baseline (Visit 2) will be logged by study clinician or delegated site staff.

5.8.4 Return or Destruction of Study Drug

At the completion of the study, there will be a final reconciliation of drug shipped, drug consumed, and drug remaining. This reconciliation will be logged on the drug reconciliation form, signed and dated. Any discrepancies noted will be investigated, resolved, and documented prior to return or destruction of unused study drug. Drug destroyed on site will be documented in the study files.

6 Study Procedures

Study Participants will be seen in the clinic for a Screening Visit within 28 days of Baseline (Visit 2 – Day 1) to assess eligibility for the study. EP participants will be randomized after eligibility is confirmed during Screening. During the screening visit, healthy controls will complete the non-patient version of the SCID while EP participants will complete the patient version of the SCID for DSM-IV-TR. In addition, EP participants will complete the BPRS rating scale per inclusion criteria and both EP participants and health controls will complete the C-SSRS. During the baseline visit, EP participants will complete all procedures. Healthy controls will receive the second ASL scan but will not receive levetiracetam, and will not have blood drawn for levetiracetam levels.

CONFIDENTIAL

This material is the property of the NYU School of Medicine and Langone Medical Center. Do not disclose or use except as authorized in writing by the study sponsor

6.1 Screening (Visit 1 – Days -28 to 0)

The following procedures will be performed at Screening:

1. The Investigator, Study MD, trained research coordinator, or the nurse practitioner will provide the participants with informed consent documents and will explain the rationale for the study.
2. Participants will be assessed for inclusion and exclusion criteria.
3. Medical history, including patient demographics, and any concomitant medications use (including over-the-counter medications, vitamins, and supplements) will be reviewed and recorded.
4. Psychiatric history will be recorded and a SCID will be conducted by the study MD or nurse practitioner. The SCID for the DSM-IV (Modules A-D) will be used to assess the primary psychiatric diagnosis for patients. Module E of the SCID for the DSM-IV will be used to assess alcohol and substance dependence/abuse (except for cannabis). Cannabis use disorder will be assessed using Module E from the SCID for the DSM-5. The other modules for the SCID will not be performed as they do not relate to the inclusion/exclusion criteria. Healthy controls will complete the non-patient version of the SCID; EP participants will complete the patient version of the SCID for DSM-IV-TR.
5. Physical examination will be completed by study MD or health nurse practitioner. Vital signs will also be completed by a trained study team member.
6. A urine pregnancy test will be performed on all females of childbearing potential.
7. A urine drug screen test will be performed.
8. In addition, the following rating scales will be completed:
 - a. Brief Psychiatric Rating Scale (BPRS) – EP Participants only.
 - b. Columbia Suicide Severity Rating Scale (CSSR-S)

Participants who are excluded from the study either due to high scores on suicidal severity screening or a cannabis use disorder will be referred to appropriate care by the study team.

6.2 Baseline (Visit 2 – Day 1)

The following procedures will be performed at Baseline:

1. A trained research assistant will complete the BPRS (EP participants only), SAFTEE and MRI safety questionnaire.
2. Optional: EP participants may decide to complete the Matrics Consensus Cognitive Battery (MCCB) to evaluate cognition.
3. Study participants will undergo a 15-minute ASL imaging scan to measure blood flow in the brain. If time permits, study participants will undergo additional ASL imaging, up to 30 minutes total, and a spectroscopy scan, up to 30 minutes, to measure chemical activity in the brain.
4. Study medication will be administered by study MD or nurse practitioner (EP participants only).
5. HC participants will also complete an additional 15-minute ASL imaging scan, and an additional spectroscopy scan, up to 30 minutes. 2 hours after the first scan is completed.
1. All participants will have their corneal, hand and temporal artery (forehead) temperature measured while seated in a chair (1 minute procedure). (optional)

CONFIDENTIAL

This material is the property of the NYU School of Medicine and Langone Medical Center. Do not disclose or use except as authorized in writing by the study sponsor

Two hours after administration of study medication, the following procedures will be performed in EP participants only:

2. A trained research assistant will complete the BPRS and SAFTEE.
3. Blood will be drawn (1 milliliter, or 0.25 teaspoons) for assay of levetiracetam levels.
4. Participants will complete a second 15-minute ASL imaging scan. If time permits, study participants will undergo additional ASL imaging, up to 30 minutes total, and an additional spectroscopy scan, up to 30 minutes.
5. Safety evaluation will be completed by study psychiatrist or nurse practitioner prior to discharge.
6. Participants will have their corneal, hand and temporal artery (forehead) temperature measured while seated in a chair (1 minute procedure). (optional)

Participants will be allowed to smoke cigarettes ad lib prior to and after imaging.

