3.1 General Design

This is a Phase 2, single-center, randomized, double-blind, placebo-controlled study to assess the tolerability and efficacy of levetiracetam. The study consists of an up to 4-week Screening period, one Baseline visit, and a follow-up telephone call the day after, as shown below. The Screening visit and Baseline visit may occur on the same day.

Sequence	Screening	Baseline	Telephone Follow-Up
Duration	Day -28 to Day 0	Day 1	Day 2

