4.2 Exclusion Criteria for EP Patients

1. Current substance abuse / dependence for substances other than nicotine and THC, (i.e. alcohol, amphetamines, barbiturates, etc.)
 - a. A positive urine toxic screen (excluding THC, tricyclic antidepressants, or benzodiazepines (if prescribed)).
 - b. Moderate or severe cannabis use disorder.
 - c. use of marijuana within the 72 hours prior to MRI scanning by self report.
2. Diagnosis of major mood disorder or other Axis I disorder other than schizophrenia, schizoaffective disorder or schizopreniform disorder.

CONFIDENTIAL

This material is the property of the NYU School of Medicine and Langone Medical Center. Do not disclose or use except as authorized in writing by the study sponsor

3. Current or recent suicidal ideation-- suicidal ideation with intent or plan (indicated by affirmative answers to items 4 or 5 of the Suicidal Ideation section of the baseline C-SSRS) in the 6 months prior to screening or subjects who represent a significant risk of suicide in the opinion of the investigator.
4. Pregnant or nursing or positive urine pregnancy test.
5. Significant medical or neurological illness by history or physical exam, including seizure disorder, history of loss of consciousness related to head trauma or developmental disorder including mental retardation.
6. Metal implants, pacemaker, or other metal in the body or medicinal patch.
7. History of claustrophobia.
8. Currently taking any antipsychotic medication (within 4 weeks).

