At the Bellevue Inpatient Psychiatry Unit, the staff will identify patients who are refusing medication and will introduce the research study to these patients. If the patients are interested in participating, [name], the Director of the Inpatient Unit, will assess the clinical appropriateness of the individual to participate in research and will assess the individual's capacity to consent. [name], a study MD/PhD or the nurse practitioner will also perform an assessment of clinical appropriateness and capacity to consent for any individuals interested in participating. After a potential study participant agrees to sign consent, the remaining screening procedures will take place on the inpatient unit at Bellevue. Following the screening procedures, individuals who qualify to participate will be transported to the NYU CBI for the Baseline procedures via ambulance as per the existing protocol at the Inpatient Unit to transport patients within NYU and Bellevue facilities for clinical procedures.

Additionally, patients will also be recruited at the Nathan Kline Institute/Rockland Psychiatric Center and Gouverneur Health. All potential study participants will be referred by clinicians – clinicians will be asked to only refer individuals who they believe are appropriate for the study, can safely delay treatment for 24 hours and who are capable of deciding to participate. Once referrals are given, the study team will access EPIC to determine the participant's initial eligibility. Subjects will also be recruited through advertisements in local newspapers. Additionally, the study team will use NYU's DataCore service to gather information from EPIC for current NYU patients who may be eligible. Fliers and brochures will be distributed by clinicians to potentially interested participants. [name] and the study coordinator will maintain relationships with clinicians at these institutions in order to generate referrals.

We will also be recruiting Spanish speaking subjects for our study. In order to recruit for Spanish speaking patients, our team will receive referrals from clinicians from our network of NYU-affiliated institutions. Clinicians who refer Spanish speaking patients will initially determine if the subject will be eligible to participate our study. If the patient qualifies and agrees to participate in our study, our team will provide a native Spanish speaking interpreter with training and understanding in medical terminology during the study visits.

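### When Screening falls on an earlier day, no suicidality scale covers the interval up to the randomised dose; a short pre-dose C-SSRS would close that gap cheaply

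*Combined protocol and SAP*

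**What the plan says.** Section 6 sets the window: "Study Participants will be seen in the clinic for a Screening Visit within 28 days of Baseline". Section 3.1 adds that "The Screening visit and Baseline visit may occur on the same day". Eligibility and allocation are tied to the first of these visits: "EP participants will be randomized after eligibility is confirmed during Screening". The schedule of events for early-psychosis (EP) patients marks both the eligibility checklist and randomisation under Screening only.

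The C-SSRS appears in the Screening list (6.1, item 8b) and has one mark in the EP schedule, under Screening. For Baseline, before study medication, 6.2 states: "A trained research assistant will complete the BPRS (EP participants only), SAFTEE and MRI safety questionnaire". An optional cognitive battery and the first scan follow, then the drug. Two hours later the BPRS and SAFTEE are repeated. Neither list contains the C-SSRS.

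Exclusion 3 in 4.2 opens with "Current or recent suicidal ideation-- suicidal ideation with intent or plan". It defines this by a yes on C-SSRS ideation item 4 or 5, with a six-month look-back that ends at screening. It also excludes "subjects who represent a significant risk of suicide in the opinion of the investigator".

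**The concern.** The exclusion is about present risk, and present risk matters most on the day the drug is given. The patients are currently psychotic, off oral antipsychotics for at least 4 weeks and as young as 16. Section 4.6 says some will be inpatients who are refusing medication. Section 1.5.1 lists rare suicidality among the reactions reported with levetiracetam. Ideation can change over days or weeks. If Screening was, say, three weeks earlier, the clinician giving the capsule has no rating of suicidality later than that.

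What is at stake is participant safety at the point of dosing: whether that clinician has a current, structured answer to a question the protocol treats as disqualifying.

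**Working it through.** The plan states no figure to reproduce. The check is where the C-SSRS sits relative to the dose, followed by the cost of adding one.

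**Placement in the randomised session**

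- *Gap between C-SSRS and dose.* Shortest: 0 days (same-day visits, 3.1). Longest: 28 days (section 6), or 29 if counted from Day -28 to Day 1 in the schedule. The distribution is not given.
- *Scales listed before the drug in 6.2.* BPRS 1, SAFTEE 1, C-SSRS 0, unless Screening is done that day.
- *C-SSRS assessments between an earlier-day Screening and the dose.* 0.
- *Period covered by the scale limb of exclusion 3.* Six months ending at Screening. The Screening C-SSRS answers this in full. The interval from Screening to dose lies outside it.
- *The phrase about a baseline C-SSRS in exclusion 3.* This could be read as the Baseline visit. Sections 6, 6.1 and 6.2 and the EP schedule all place the scale at Screening, so the phrase does not put one on the dosing day. It does need clarifying.

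**Cover that does not depend on the scale**

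- The judgement limb of exclusion 3 needs no instrument, and a physician or nurse practitioner gives the drug (6.2).
- Section 8.1 counts any symptom that appears or worsens during the study as an adverse event, with reporting from the first study procedure. New ideation after Screening would qualify, and 8.2 requires specific questioning at every contact. Whether this happens before or after the dose is not stated.
- Section 4.9 lets the investigator discontinue a patient on health or well-being grounds.
- For outpatients screened remotely, 4.7.1 requires that "it has been determined that participants meet all IEC for the study" before Baseline procedures begin. The assessments it moves to that visit are vital signs, anthropometrics, physical examination and urine. The C-SSRS is not among them, and the section is written for remote visits.
- The safety evaluation in 6.2 and the psychiatric clearance in 1.5.2 both precede release, so they follow the drug.

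**Cost of one added C-SSRS**

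Input: 24 to 46 EP patients randomised (5.2). Minutes per scale and the share screened on an earlier day are assumptions.

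- Everyone screened earlier: at most 1 × 24 = 24 to 1 × 46 = 46 administrations.
- Half screened earlier: 0.5 × 24 = 12 to 0.5 × 46 = 23.
- A quarter: 0.25 × 24 = 6 to 0.25 × 46 = 11.5, rounded to 12.
- Maximum hours at 5 minutes: 24 × 5/60 = 2.0 to 46 × 5/60 = 3.8.
- Range at 3 to 10 minutes: 24 × 3/60 = 1.2 to 46 × 10/60 = 7.7 hours.

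**The case against.** The best reply is that nothing in exclusion 3 is left undone. Its scale limb ends at Screening and is met there; its judgement limb remains open to the clinician at dosing. This stands. A reader might infer that the protocol fails to apply its own criterion, or doses patients it defines as ineligible. The documents do not support that. The gap is an interval that the scale limb was never written to reach.

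A reader might also infer that nobody asks about suicidality before the dose. That goes too far, given the cover set out above. Section 1.5.2 also speaks of excluding people with a history of suicidality. Referring clinicians are asked to choose patients who "can safely delay treatment for 24 hours and who are capable of deciding to participate", which suggests short gaps for many. None of this shortens the permitted window or fixes a structured question before the drug.

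Two comparisons are tempting but weak. The BPRS is repeated at Baseline, but it is given before and after the dose and so serves as a pre/post measure; nothing says it re-checks eligibility. Section 6.4 lists a C-SSRS in the optional repeat session, but alongside a fresh history, physical examination, pregnancy test and drug screen. That is a re-screening set at least two weeks later, not a dosing-day standard that 6.2 breaks.

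Finally, exposure is one dose, and section 8.1 regards psychiatric reactions to it as highly unlikely. That also stands. The case here rests on the patient's state before the drug and makes no claim about detecting drug effects afterwards.

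**Conclusion.** The point holds as a minor participant-safety improvement. For patients screened on an earlier day, the interval up to dosing (at most 28 days by section 6) has no suicidality scale. The clinical safeguards are real, but none guarantees a structured check before the drug. The gap matters most for patients screened in person on an earlier day, because the Baseline eligibility review in 4.7.1 is not written for them.

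The size of the benefit cannot be stated: the documents give neither the distribution of the gap nor the rate of new ideation within it. If most patients are screened and dosed on the same day, both the gap and the cost of closing it are close to nil. The perfusion endpoint, the effect-size threshold and the go/no-go rule are unaffected, and a reader should not infer any bias in the result.

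**What to change.** In 6.2, before the step that gives study medication, add: if Screening was on an earlier day, complete a C-SSRS covering the time since Screening, to be reviewed by the study physician or nurse practitioner before dosing. State the dosing rule directly: withhold or defer if ideation item 4 or 5 is answered yes for the period since Screening, or if the clinician judges there is a significant suicide risk; then refer to care as 6.1 already provides. Pointing back to exclusion 3 would not work, because its six-month window closes at Screening.

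Mark the C-SSRS at Visit 2 in the EP schedule, and make clear in exclusion 3 that the baseline C-SSRS means the Screening assessment plus this pre-dose update.

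The cost is a few minutes per patient, using a scale, staff and a visit already in the study. Now and then a patient will be randomised but not dosed. Section 7.2 analyses those who receive study drug, so that patient drops out of the analysis and must be replaced to reach 8 eligible completers per group. Each such case uses one of the 46 randomisation slots in 5.2. With 3 × 8 = 24 completers needed, 46 − 24 = 22 slots are available for losses of every kind.
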